##### **3.2.1.3. Vital Sign Measurements**

A single measurement of pulse rate and supine systolic and diastolic blood pressure (BP) will be taken at the times specified in the protocol.

Baseline will be the last pre-dose measurement in each study period. Change from baseline will be calculated for all post-baseline timepoints.

##### **3.2.1.4. Laboratory Measurements**

Safety laboratory tests (hematology, chemistry, and other clinical laboratory tests) will be performed as described in the protocol. Baseline will be the last pre-dose measurement in each study period. Change from baseline will be calculated for all post-baseline timepoints.

To determine if there are any clinically significant laboratory abnormalities, the safety laboratory tests will be assessed against the criteria specified in the sponsor reporting standards. The assessment will take into account whether each participant's baseline test result is within or outside the laboratory reference range for the particular laboratory parameter.

### 3.2.2. Baseline adjusted QTcF of moxifloxacin and placebo at $T_{max}$ of 3, 4, and 5 hours on Day 3.

Change from baseline QTcF for each participant at 3, 4, and 5-hours post dosing on Day 3 in the treatment periods of moxifloxacin and placebo will be calculated. See [Section 3.1.1](#) for baseline and calculation details.

### 3.3. Other Endpoint(s)

#### 3.3.1. Baseline adjusted heart rate, PR interval, and QRS intervals of sisunatovir and placebo at each postdose time point.

Changes from baseline in heart rate, PR interval, and QRS interval of each participants in the treatment periods of sisunatovir and placebo at each postdose time point will be calculated. See [Section 3.1.1](#) for baseline and calculation details.

#### 3.3.2. Plasma sisunatovir parameters, including $C_{max}$ , $T_{max}$ and area under the plasma concentration-time profile from time 0 to 24 hours (AUC24) post-dose on Day 3.

*Blood samples for the PK analysis of sisunatovir will be collected following the 0 hour and post-dose ECG measurements at the same time-points on Day 3 for each treatment as specified in the protocol.*

The PK parameters of sisunatovir to be derived (if data permit) from the concentration-time data using standard noncompartmental methods are defined in Table 2. Actual PK sampling times will be used in the derivation of PK parameters. In the case that actual PK sampling times are not available, nominal PK sampling time will be used in the derivation of PK parameters.

**Table 2. Noncompartmental PK Parameters**

Parameter	Analysis Scale	Sisunatovir
AUC 24	ln	D
$C_{max}$	ln	D
$T_{max}$	R	D

Key: ln=natural-log transformed, R=raw (untransformed),  
D=displayed with descriptive statistics, A=analyzed using statistical model

#### 3.3.3. Concentration of sisunatovir from paired samples obtained via microsampling compared to venous sampling.

Day 2 PK samples (traditional venous collection) and time matched PK microsamples (dried blood using the Tasso® M20 device) will be collected in Period 1 only at time points specified in the SoA of the protocol. Furthermore, at the 5 hour and 12-hour time point on Day 2, an aliquot of the PK blood sample collection will be taken and used to determine the concentration of sisunatovir in whole blood.

For each individual, blood to plasma (B/P) ratios will be calculated by dividing concurrent (i.e. Day 2, at 5 hour and 12 hour post-dose) whole blood sisunatovir concentration with the plasma sisunatovir concentration and the geometric mean B/P ratio will be calculated. A

population geometric mean of the B/P ratio from all individuals will also be calculated. Missing values will not be imputed. The plasma equivalent sisunatovir concentration by microsampling will be calculated by dividing the whole blood sisunatovir concentration with the individual geometric mean B/P ratio. As a sensitivity analysis, the plasma equivalent concentration will also be calculated using the population geometric mean B/P ratio.  $AUC_{12}$  and  $C_{max}$  will be derived from blood samples collected using the Tasso® M20 device, and then adjusted for B/P ratio.

### 3.4. Baseline Variables

- Baseline QTcF covariate for c-QT analysis

Baseline will be defined as the mean of the 3 average triplicate measurements taken at approximately 40 min, 25 min, and 10 min before the pre-dose meal on Day 1 within each period. Denote the baseline QTcF of participant  $i$  in treatment  $j$  at time 0 as  $\overline{QTcF}_{ij0}$ . The centered baseline,  $QTc_{ij0} - \overline{QTc}_0$  will be used in the c-QT analysis, where  $\overline{QTc}_0$  is the *overall mean of  $QTcF_{ij0}$ , i.e., the mean of all the baseline (= time 0) QTcF values* from all participants. More details will be documented in a separate report and included as an Appendix to the CSR.

- Baseline ECG covariate for MMRM analysis

The pre-dose baselines (one for each treatment period) will be included as covariate in the MMRM analysis of ECG parameters.

### 3.5. Safety Endpoints

See [Section 3.2.1](#).

## 4. ANALYSIS SETS (POPULATIONS FOR ANALYSIS)

Data for all participants will be assessed to determine if participants meet the criteria for inclusion in each analysis population prior to unblinding and releasing the database and classifications will be documented per standard operating procedures.

Population	Description
Enrolled	“Enrolled” means a participant’s, or their legally authorized representative’s, agreement to participate in a clinical study following completion of the informed consent process and randomization. A participant will be considered enrolled if the informed consent is not withdrawn prior to participating in any study activity after screening. Potential participants who are screened for the purpose of determining eligibility for the study, but do not participate in the study, are not considered enrolled, unless otherwise specified by the protocol.

Population	Description
ECG analysis set	All participants randomized and treated who have at least 1 post-dose ECG measurement in at least 1 period. Analysis sets may contain different numbers of participants for different ECG parameters based on availability of data. Participants will be analyzed according to the product they actually received.
Concentration-QTc analysis set	The concentration QTc analysis population is defined as all participants randomized and treated with sisunatovir or placebo who have at least 1 pair of time-matched post-dose QT and sisunatovir plasma concentration values in at least 1 period of the study. For placebo treatment, the concentration is set to 0.
PK Concentration analysis set	All participants randomly assigned to study intervention and who take at least 1 dose of study intervention and in whom at least 1 concentration value can be reported.
PK Parameter analysis set	All participants randomly assigned to study intervention and who take at least 1 dose of study intervention and in whom at least 1 of the PK parameters of interest can be reported.
Safety analysis set	All participants randomly assigned to study intervention and who take at least 1 dose of study intervention. Participants will be analyzed according to the product they actually received.

## 5. GENERAL METHODOLOGY AND CONVENTIONS

### 5.1. Hypotheses and Decision Rules

#### 5.1.1. Hypotheses and Decision Rules of the Primary Endpoint

Concentration-QTc analysis will be used to assess if sisunatovir at maximum concentrations (Cmax) at the ~~CCI~~ has clinically relevant effect on the QTc interval at one sided  $\alpha = 0.05$  level without multiplicity adjustment. After a final concentration- $\Delta$ QTc model has been established, denote the population mean of model predicted placebo-corrected  $\Delta$ QTcF ( $\Delta\Delta$ QTcF) at the Cmax of a dose of interest as  $\mu_{cmax}$ , the null hypothesis of sisunatovir having a positive QTc effect and the alternative hypothesis of sisunatovir having a negative QTc effect at the dose of interest can be expressed as the following:

$$H_0: \mu_{cmax} \geq 10 \text{ msec}$$

$$H_a: \mu_{cmax} < 10 \text{ msec}$$

The lack of effect of sisunatovir on QTc intervals will be concluded if the upper bound of the 2-sided 90% CI for the  $\Delta\Delta$ QTcF estimated by the final concentration- $\Delta$ QTc model is  $< 10$  msec at the highest clinically relevant exposure.

#### 5.1.2. Hypotheses and Decision Rules of Assay Sensitivity

The assay sensitivity is tested at 3, 4 and 5-hours post-dose of positive control, moxifloxacin,

on Day 3 simultaneously at one-sided  $\alpha = 0.05$  level with Bonferroni correction of  $\alpha/3$  for multiple assessments. Denote the population mean of change from baseline in QTcF of moxifloxacin and placebo at 3, 4, or 5-hr post-dose as  $\mu(M)$  and  $\mu(P)$ , respectively, the statistical hypotheses are:

$$H_0: \mu(M) - \mu(P) \leq 5 \text{ msec}$$

$$H_a: \mu(M) - \mu(P) > 5 \text{ msec}$$

The study will be deemed adequately sensitive to detect QT/QTc prolongation if any of the lower limits of the two-sided Bonferroni-adjusted 90% CI (96.7% CI) for mean differences between moxifloxacin and placebo at any of the 3, 4 and 5-hr pose-dose, respectively, are greater than 5 msec.

## 5.2. General Methods

The analyses related to the primary, secondary and exploratory endpoints will be based on the appropriate population for analysis (see [Section 4](#)).

Unless otherwise stated, all summaries and plots will be presented by treatment group. The following treatment group labels (or similar) will be used:

- Placebo
- Sisunatovir
- Moxifloxacin

In this study, an initial dose of CCI has been selected to achieve high clinical exposure. If observed exposure of CCI is lower than predicted and do not cover the high clinical exposure, then the dose will be increased to CCI. If the dose of CCI is selected, the sisunatovir treatment group will include participants in both CCI mg and CCI mg CCI doses.

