### 6.2.1.2. ECG assessments

Absolute values and changes from baseline for the ECG parameters (ie, HR, PR interval, QT interval, QTcF, QTcB, and QRS complex) will be summarized by treatment group and timepoint according to sponsor reporting standards. Tables will be paged by parameter.

Maximum absolute values and changes from baseline for QTcF, QTcB, PR, and QRS, as well as the maximum and minimum absolute values of HR, will also be summarized descriptively by treatment group using categories as defined in [Appendix 1](#). Numbers and percentages of participants meeting the categorical criteria will be provided. All planned and unplanned postdose timepoints will be counted in these categorical summaries.

*If any of the 3 individual ECG tracings has a QTcF value  $\geq 500$  msec, but the mean of the triplicates is  $< 500$  msec, the data from the participant's individual tracing will be described in a safety section of the study report in order to place the  $< 500$  msec value in appropriate clinical context. However, values from individual tracings within triplicate measurements that are  $\geq 500$  msec will not be included in the categorical analyses unless the average from the triplicate measurements is also  $\geq 500$  msec.*

Individual participant profiles will be created for those participants meeting the sponsor's abnormality criteria – including absolute values, change from baseline and percent change from baseline. Listings of participants with any single post dose value  $> 500$  msec will also be produced for QTcF.

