### 6.2.1.3. Vital sign measurements

Absolute values and changes from baseline in supine systolic and diastolic BP, and PR will be summarized by treatment group and timepoint, according to sponsor reporting standards. Tables will be paged by parameter.

Maximum decrease from baseline for supine systolic and diastolic blood pressures and maximum increase from baseline for supine pulse rate will be summarized by treatment group, according to sponsor reporting standards.

Maximum absolute values and changes from baseline for vital signs will also be summarized descriptively by treatment group using categories as defined in [Appendix 1](#). Numbers and percentages of participants meeting the categorical criteria will be provided. All planned and unplanned post dose time points will be counted in these categorical summaries. All values meeting the criteria of potential clinical concern will be listed.

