### 6.2.1.4. Clinical safety laboratory measurements.

Laboratory data will be listed and summarized by treatment group and overall, in accordance with the sponsor reporting standards.

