#### **6.3.2. Plasma sisunatovir parameters, including $C_{max}$ , $T_{max}$ and area under the plasma concentration-time profile from time 0 to 24 hours ( $AUC_{24}$ ) post-dose on Day 3.**

The PK parameter listed in the Table 3 will be summarized descriptively by treatment.

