**Table 3. PK Parameters**

Parameter	Summary Statistics
$C_{max}$	N, arithmetic mean, median, cv%, standard deviation, minimum, maximum, geometric mean and geometric cv%.
$T_{max}$	N, median, minimum, maximum.

AUC 24	N, arithmetic mean, median, cv%, standard deviation, minimum, maximum, geometric mean and geometric cv%.
AUC 12 *	N, arithmetic mean, median, cv%, standard deviation, minimum, maximum, geometric mean and geometric cv%.

\*To be comparable with Microsampling.

Box and whisker plots for individual subject parameters (AUC24 and Cmax) will be presented and overlaid with geometric means.

Presentations for sisunatovir concentrations will include:

- a listing of all concentrations sorted by subject ID and nominal time postdose. The concentration listing will also include the actual times. Deviations from the nominal time will be given in a separate listing.
- a summary of concentrations by nominal time postdose, where the set of statistics will include n, mean, median, standard deviation, coefficient of variation (cv), minimum, maximum and the number of concentrations above the lower limit of quantification.
- median concentrations time plots (on both linear and semi-log scales) against nominal time postdose (based on the summary of concentrations by time postdose).
- mean concentrations time plots (on both linear and semi-log scales) against nominal time postdose (based on the summary of concentrations by time postdose).
- individual concentration time plots by treatment (on both linear and semi-log scales) against actual time postdose.
- individual concentration time plots by subject (on both linear and semi-log scales) against actual time postdose (there will be separate plots for each subject per scale).

For summary statistics, median and mean plots by sampling time, the nominal PK sampling time will be used, for individual subject plots by time, the actual PK sampling time will be used.

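### If the sisunatovir dose is raised mid-study, the SAP pools both doses into one group and plans no by-dose PK, ECG, vital-sign or laboratory summaries

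*SAP*

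**What the plan says.** Protocol 4.3 and 6.6 provide for one increase in the sisunatovir dose after review of safety and PK in about the first 7 participants (4.3 also says at least 7). Protocol 4.3 adds that projected exposure at the higher dose may be no more than 20% above the mean rat NOAEL exposure.

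SAP 5.2 sets the default: "Unless otherwise stated, all summaries and plots will be presented by treatment group". It lists three labels (placebo, sisunatovir, moxifloxacin, or similar). It then says that after an increase "the sisunatovir treatment group will include participants in both" doses.

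The later sections do not depart from that default:

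- PK parameters (SAP 6.3.2) "will be summarized descriptively by treatment".
- Concentrations (SAP 6.3.2) get "a summary of concentrations by nominal time postdose", and the mean and median profiles are built on it.
- "Box and whisker plots for individual subject parameters" are planned with geometric means overlaid, with no split by dose.
- ECG parameters (SAP 6.2.1.2) "will be summarized by treatment group and timepoint according to sponsor reporting standards".
- Vital signs (SAP 6.2.1.3): "Maximum absolute values and changes from baseline for vital signs will also be summarized descriptively by treatment group using categories as defined in" Appendix 1.
- Laboratory tests (SAP 6.2.1.4): "Laboratory data will be listed and summarized by treatment group and overall, in accordance with the sponsor reporting standards".

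SAP 6.2.1.1 refers adverse events to sponsor standards without naming a grouping. SAP 6.4 says there will be no subset analyses.

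**The concern.** Protocol 2.2.4, 4.2 and 4.3 state that exposure rises more than in proportion to dose, so a pooled geometric mean mixes two distinct exposure levels. Day 3 Cmax, Tmax and AUC24 are a named exploratory endpoint. The protocol's dose reasoning is itself dose-specific: Table 3 has separate predicted columns for 250 mg and 300 mg, and the increase is triggered by exposure at the initial dose falling short of prediction. A pooled summary can be set against neither column. No planned summary would show the exposure that triggered the increase or the exposure achieved after it.

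Safety and tolerability is a secondary objective, and Protocol 2.2.4 reports gastrointestinal events as more frequent at 350 mg than at 200 mg. Pooled ECG, vital-sign and laboratory tables would not show whether findings cluster at one dose.

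**Working it through.** The plan gives no figure to reproduce here, because the study doses and predicted exposures are redacted. The following is an illustration.

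**Inputs from Protocol Table 3.** Geometric mean Cmax (geometric CV) is 97.9 ng/mL (65%) at the lower observed dose and 811.0 ng/mL (41%, n=5) at the higher. Rat NOAEL Cmax is 322 ng/mL.

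**Assumptions.** Study doses are 250 mg and 300 mg (the Table 3 column heads). The lower observed dose is 200 mg. Interpolation is log-log. The share on the initial dose is f = 7/42.

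**Formulas.** With exponent b, the ratio of initial to raised geometric mean is r = (250/300)^b.

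- Pooled / raised geometric mean = r^f.
- Pooled / initial geometric mean = r^(f-1).
- Pooled geometric CV = sqrt(exp(s² + f(1-f)(ln r)²) - 1), with s² = ln(1 + CV²).

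**Low end: dose-proportional, b = 1.** r = 0.833. Pooled / raised = 0.833^(1/6) = 0.970 (3% below). Pooled / initial = 0.833^(-5/6) = 1.164 (16% above).

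**High end: projected Cmax at 300 mg just meets the protocol limit.** The limit is 1.2 × 322 = 386.4 ng/mL. b = ln(386.4/97.9)/ln(1.5) = 3.39, so r = 0.539. This corresponds to an upper observed dose of about 373 mg. Pooled / raised = 0.902 (10% below). Pooled / initial = 1.673 (67% above).

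**Between the two.** With the upper observed dose at 525 mg, the highest in the completed studies (Protocol 2.2.4), b = ln(811.0/97.9)/ln(525/200) = 2.19 and r = 0.671. The pooled mean is 6% below the raised value and 40% above the initial value.

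**Effect on reported variability.** A within-dose Cmax CV of 41% would be reported as 42-48%, and 65% as 66-71%.

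**If more than 7 receive the initial dose.** With 14 of 42, the pooled mean is 6-19% below the raised value (0.833^(1/3) = 0.941; 0.539^(1/3) = 0.814). With 21 of 42 it is 9-27% below (0.913; 0.734).

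**Sampling error for scale.** The 90% CI of a geometric mean is exp(±t·s/√n). At CVs of 41% and 65% it is -10%/+11% and -14%/+17% for n=42, and -25%/+34% and -35%/+55% for n=7.

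**AUC limit.** The protocol limit refers to exposure in general, and the rat AUC covers 24 hours. If twice the 12-hour AUCtau must also stay within 1.2 × 4725 = 5670 ng·h/mL, then b for AUC is at most ln(2835/787.3)/ln(1.5) = 3.16. AUC is then at most 9% below and 62% above. The matching upper observed dose, about 404 mg, gives a Cmax b of 3.01, so the Cmax high end falls to 9% and 58%. The 3-10% and 16-67% ranges are therefore on the generous side.

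**Model-based QTc analyses.** The primary model in SAP 5.2.3 regresses ΔQTcF on each participant's measured concentration, so a second dose widens the exposure range and does not blur it. Assay sensitivity (SAP 5.1.2) compares moxifloxacin with placebo. The supplementary by-time MMRM (SAP 6.1.1.2) does use the pooled group. If the raised dose truly gave 10 msec on a linear slope, the pooled estimate would be low by (7/42) × 10 × (1 - r) = 0.3 to 0.8 msec, and by nothing if the slope is flat.

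**The case against.** The strongest case on the other side is that this is table layout, in a contingency that may never arise, announced in advance, with no test affected. The label list allows similar labels, so by-dose display is not forbidden. An increase requires a look at about the first 7 participants by an unblinded sponsor, so initial-dose data are examined before it. Doses given are confirmed and recorded (Protocol 6.5). The listings, individual profiles and box plots of individual parameters keep the information available. The shift from the raised-dose value is mostly within sampling error, and a column of about 7 is itself imprecise.

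Most of this stands and sets the severity. It does not remove the point. The sentence after the label list specifies pooling, the review of the first 7 promises no report table, and SAP 6.3.2 does not say the concentration listing shows dose. Imprecision argues for cautious reading of a small column. Protocol Table 3 itself reports a dose group of 5.

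A reader might go further in three ways that the documents do not support:

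- **That adverse events will also be pooled.** SAP 6.2.1.1 names no grouping, so this is unknown. ECG, vital-sign and laboratory outputs also cite sponsor standards, but their sections do name treatment group.
- **That pooling undermines the QTc conclusion.** The primary model and the assay-sensitivity comparison do not depend on the grouping.
- **That the distortion could reach 11% below and 78% above.** That needs an upper observed dose of 350 mg, which projects 97.9 × 1.5^3.78 = about 453 ng/mL at 300 mg, above the protocol's own limit of 386 ng/mL.

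**Conclusion.** The point holds as a minor one, at the low end of minor. After a dose increase, the SAP as written would give PK summaries and ECG, vital-sign and laboratory tables that mix two doses of a drug with more than dose-proportional exposure. The pooled Cmax would sit close to the raised-dose value (about 3-10% below) and well above the initial-dose value (about 16-67%).

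Confidence in the reading of the SAP is high. Confidence in the figures is not: they rest on assumed doses, an assumed interpolation, an upper anchor with n=5 and 7 of 42 on the initial dose. An increase prompted by lower-than-predicted exposure would also mean that the interpolation had mispredicted.

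**What to change.** Amend SAP 5.2, 6.2.1 and 6.3.2 to say that, if both doses are used, PK parameters, concentration profiles and safety summaries (adverse events, ECG, vital signs, laboratory) are also shown descriptively by actual dose received, beside the pooled column. State that SAP 6.4 does not exclude these displays. Leave the concentration-QTc model, the assay-sensitivity test and the by-time MMRM unchanged.

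The cost is a few sentences and extra table columns, with no effect on alpha, sample size or dosing. The initial-dose column may hold only about 7 participants, and dose is confounded with enrolment order, so the columns should be labelled descriptive and not used to compare doses. Writing this in before data are seen is preferable in a sponsor-open study.

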### 5.2.1. Analyses for Continuous Endpoints

Unless otherwise stated, continuous variables will be presented using summary statistics: number of observations, arithmetic mean, standard deviation (SD), median and range (minimum and maximum) values. For endpoints to be analyzed on the natural log scale (loge), the geometric mean and geometric coefficient of variation (CV) will additionally be calculated.

